APPENDIX 4 DEFINITIONS OF CAUSALITY AND SEVERITY OF ADVERSE EVENTS

APPENDIX 5 DECLARATION OF HELSINKI 2008

PROTOCOL SYNOPSIS

Title	A Phase IIa, prospective study to evaluate the safety and efficacy of anti- Chlamydophila antibiotic combination (ACAC) therapy comprising 100mg doxycycline, 500mg azithromycin and 300mg rifabutin in the treatment of patients with Coronary Heart Disease (CHD)
Study Sites	Liverpool Hospital/ Sydney Southwest Private Hospital
Objectives	
Primary objectives:
 
 1. To evaluate the effect of an antibiotic combination therapy on fractional flow reserve (FFR) (coronary arterial flow) in participants with Coronary Heart Disease 
Secondary objectives:
 
 1. To evaluate the effect of an antibiotic combination therapy on plaque morphology and volume as assessed with intra-coronary imaging (IVUS and/or OCT) in culprit and non-culprit arteries in a substudy 2. To evaluate angiographic stenoses changes using Quantitative Coronary Angiography (QCA) during ACAC therapy. 3. To evaluate morbidity and clinical improvement during the ACAC therapy. 4. To record major adverse clinical events (MACE). Including death, recurrent myocardial infarction, stroke and major bleeding. 
Exploratory objectives:
 
 1. To evaluate the use of loop-mediated isothermal amplification (LAMP) for the detection of Chlamydophila pneumoniae in blood samples, compared with standard titers and cell culture 2. To evaluate changes in indices of pressure and flow (as measured with coronary pressure/flow guidewire) in culprit and non-culprit coronary arteries
Design	Phase IIa, multicenter, randomised, placebo-controlled trial
Population	Subjects with symptomatic coronary heart disease on medical therapy who have a culprit artery lesion suitable for percutaneous coronary intervention (PCI) and another stenosis potentially suitable for staged PCI, with FFR ≤ 0.80 . Or subjects who have a single non-culprit artery of intermediate severity with a clinically indicated FFR ≤ 0.80 which is suitable for staged PCI.
Sample Size	60 subjects
Treatment	All subjects will be assigned to either active treatment or matching placebo. They will receive ACAC in conjunction with standard medical therapy for 3 months.
Efficacy Data	FBC, ESR, Electrolytes/Urea/Creatine, Liver Function tests, Lipid Studies ,CK-MB, High Sensitivity Troponin T, Chlamydophila pneumoniae titer, Chlamydophila pneumoniae macrophage culture, Chlamydophila pneumoniae (c. pneumoniae) DNA detection (exploratory), hs CRP, symptomatology, Functional Status – New York Heart Association Class, Quantitative Coronary Angiography (QCA); FFR and Coronary pressure/flow indices, plaque volume, plaque composition, fibrous cap thickness, macrophage content.
Safety data	Adverse event reports, Blood tests (standard haematology, serum chemistry and pregnancy) and Physical Examination, compliance and major adverse cardiac events MACE
Statistical procedures	Results will be presented as mean +/-SD for continuous normally distributed variables, as median (interquartile range) for continuously non-normally distributed data and as percentages for categorical data. Significant changes in clinical symptom improvement, arterial flow and biochemical variables over time will be assessed using ANOVA for repeated measurements. A P value < 0.05 will be considered statistically significant.
Study duration & dates	Total of 24-month recruitment period. From Q1 - 2018 to Q3 - 2019. Study duration is 6 months from the initial angiographic procedure

PATIENT FLOW DIAGRAM

STUDY SCHEDULE

Assessments and Recordings	V1	V2	Phone Call	V3	Phone Call	Phone Call	V4
	Screening and Baseline	Day 30 (+7 days)	Day 60	Day 90 (+21 days)	Day 120	Day 150	Day 180 (+ 21 days)
Subject Information	X						
Informed Consent	X						
Inclusion/Exclusion Criteria	X						
Demographics	X						
Medical History	X						
Confirmation of eligibility	X						
Laboratory tests							
FBC	X	X		X			
ESR	X	X		X			
EUC	X	X		X			
Liver Function Tests	X	X		X			
Lipid Studies	X	X		X			
CK-MB	X	X		X			
High Sensitivity Troponin T	X	X		X			
High Sensitivity CRP	X	X		X			
Pregnancy testing	X						
C. pneumoniae macrophage cultures	X			X			
C. pneumoniae titers	X			X			
C. pneumoniae DNA detection	X			X			
Physical Examination	X	X		X			
Vital Signs	X	X		X			
Quantitative Coronary Angiogram	X			X			
ECG	X			X			
New York Heart Association Functional Class	X	X		X			
Fractional Flow Reserve, Pressure/flow wire measurements and intracoronary imaging (IVUS + OCT)	X			X			
Concomitant medications	X	X	X	X	X	X	X
Concomitant illnesses	X	X	X	X	X	X	X
Medication dispense/collection	X			X			
Medication review/Accountability		X		X			
Participant Symptomatology Diary	X	X		X			X
Adverse events	X	X	X	X	X	X	X

ABBREVIATIONS AND DEFINITIONS

ACAC	Anti-Chlamydomphila Antibiotic Combination
ACS	Acute Coronary Syndrome
AE	Adverse Event
CANTOS	Canakinumab Antiinflammatory Thrombosis Outcome Study
CDD	Centre for Digestive Diseases
CAD	Coronary Artery Disease
CHD	Coronary Heart Disease
CK-MB	Creatine Kinase MB
CRF	Case Report Form
CRP	C-Reactive Protein
CTN	Clinical Trials Notification (Scheme)
ECG	Electrocardiogram
EOT	End of Trial
EUC	Electrolytes, Urea, Creatinine
FBC	Full Blood Count
FFR	Fractional Flow Reserve
GCRP	Good Clinical Research Practice
HREC	Human Research Ethics Committee
HMR	Hyperaemic Microvascular Resistance
HSR	Hyperaemic Stenosis Resistance
ICH	International Conference for Harmonisation
IMR	Index of Microvascular Resistance
IVUS	Intra-Vascular Ultrasound
JUPITER	Justification for the Use of statins in Primary prevention: an Intervention Trial Evaluating Rosuvastatin
LAMP	Loop-mediated isothermal amplification (of DNA)
LDL	Low density lipoprotein

MACE	Major Adverse Cardiovascular Events
NHMRC	National Health and Medical Research Council
OCT	Optical Coherence Tomography
PCI	Percutaneous Coronary Intervention
SAE	Serious Adverse Event
SD	Standard Deviation
TGA	Therapeutic Goods Administration
TWAR	Taiwan Acute Respiratory Agent
QCA	Quantitative Coronary Angiography
V1	Visit 1
V2	Visit 2
V3	Visit 3
V4	Visit 4

For Laboratory tests please see Appendix 1.

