7.2.1.1 Laboratory Studies

Efficacy of combination therapy will be assessed using blood samples collected at each visit. The following tests will be performed: FBC, ESR, lipid studies, liver function. In addition the following will be performed:

High Sensitivity C-Reactive protein (Hs-CRP) is a protein in the blood that increases in the presence of inflammation. Hs-CRP will measure the small amounts of CRP produced by the long-term inflammation from atherosclerosis.

- 4ml of blood will be collected in an EDTA tube. This sample will then be transferred to the laboratory for a full blood count
- 4ml of blood will be collected in an SST/Gel tube and transferred to the laboratory for liver function tests, Cholesterol, triglyceride studies and hs-CRP.
- 4ml of blood will be collected in a lithium heparin tube. Sample will then be transferred to the laboratory for CK-MB, Troponin T tests and UEC testing.
- 5ml of blood will be collected in a special ESR collection tube. This will then be sent to the laboratory to test the ESR
- 2 x 4ml of blood will be collected in citrated tubes. This sample will be transferred to the laboratory for *C. pneumoniae* detection by macrophage culture and *C. pneumoniae* titer determination (Visit 1 and 3 only).
- 3 x 4ml (i.e. 12 ml) of blood will be collected in an EDTA tube. This sample will be transferred to the laboratory for *C. pneumoniae* DNA detection by LAMP (Visit 1 and 3 only).

The total blood drawn on at Visit 1 and Visit 3 will be approximately 40mls. The total blood drawn at Visit 2 will be approximately 20 ml.

Blood samples will be tested by an experienced pathologist at Lavery Pathology for all tests excluding *C. pneumoniae* DNA detection by LAMP (exploratory research) and *C.pneumoniae macrophage cultures*.

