11. STATISTICAL PROCEDURES

11.1 *Analysis Variables*

Analysis of efficacy will be performed according to intention-to-treat method and include all subjects who received the combination antibiotic therapy. However as the primary efficacy analysis is of subjects with paired FFR assessments, only such subjects will be included in the primary analysis. All other subjects will be included in secondary analyses. Numerical data will be presented as mean \pm SD for normally distributed variables and as median with interquartile range for non-normally distributed data. Non-normally distributed data will be log-transformed (e.g. CRP levels) before being used for comparisons. Significant changes in subjects' arterial flow, clinical symptoms and biochemical variables over time compared with that baseline will be assessed using an analysis of covariance. Differences between treatment and control groups in the occurrence of FFR \geq 80 will be assessed using Fisher's exact test. All tests will be 2-tailed with a 5% significance level.

11.2 *Interim Analysis*

A DSMB directed interim analysis is planned when 60 paired FFR data are available. At this time point, the trial would declare the combination therapy as effective if the p value is less than 0.05. However, the trial might still continue to collect extra data to accurately characterise side effects as advised by the DSMB.

11.3 *Sample Size Justification*

This is a feasibility study designed to provide preliminary observations and generate hypothesis for future studies. The sample size of 60 subjects with paired FFR was not defined on the basis of a clinical endpoint hypothesis but rather to provide information about antibiotic combination therapy efficacy and safety. The sample size required is established by assessment of the minimum number of subjects needed to provide reliable and non-trivial results. The sample size is in the range of the intervention group in the azithromycin clinical trial of subjects with CAD (n=60).

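### One unqualified 5% significance rule covers every test, so secondary and exploratory results of a hypothesis-generating study can be called significant without multiplicity control

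*Combined protocol and SAP*

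**What the plan says.** The Efficacy Data row of the protocol synopsis lists 20 items, in three runs:

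- Seven laboratory items: "FBC, ESR, Electrolytes/Urea/Creatine, Liver Function tests, Lipid Studies ,CK-MB, High Sensitivity Troponin T".
- Six more: *C. pneumoniae* titer, macrophage culture and DNA detection, followed by "hs CRP, symptomatology, Functional Status" (the last by NYHA class).
- Seven physiological and imaging items: "Quantitative Coronary Angiography (QCA); FFR and Coronary pressure/flow indices, plaque volume, plaque composition, fibrous cap thickness, macrophage content".

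The Statistical procedures row names the outcome groups to be tested: "Significant changes in clinical symptom improvement, arterial flow and biochemical variables over time will be assessed using ANOVA for repeated measurements". It then gives a single rule, that a P "value < 0.05 will be considered statistically significant". Section 11.1 has a similar sentence about change from baseline in the same three groups, using analysis of covariance. It assigns Fisher's exact test to the between-group FFR comparison and ends: "All tests will be 2-tailed with a 5% significance level". Section 7.2.1.1 adds that "Efficacy of combination therapy will be assessed using blood samples collected at each visit".

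Section 3 defines one primary endpoint, based on FFR. Sections 2.1 to 2.3 rank the objectives as primary, secondary and exploratory. Section 11.3 states: "This is a feasibility study designed to provide preliminary observations and generate hypothesis for future studies". The documents contain no multiplicity adjustment, no testing order and no statement that secondary p-values are descriptive.

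**The concern.** The protocol ranks its objectives, but the significance rule ignores the ranking. A chance shift in a liver enzyme or a symptom score would earn the same label as a positive primary result. The purpose in Section 11.3 is to pick out what deserves further study. A list of results marked significant, with no account of how many were examined, is poor guidance for that.

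The wording about change over time adds a second route to such labels. Neither the synopsis sentence nor its counterpart in Section 11.1 says that the arms are compared. Section 4.1 admits subjects with a recent acute coronary syndrome, and Section 1.1 accepts that non-culprit FFR may be temporarily worse in that setting. Recovery alone could then produce a significant change from baseline in both arms.

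**Working it through.** **The plan's own figure.** The only error rate stated is 0.05 per test, and the synopsis and Section 11.1 agree on it. No family-wise rate is given, so there is none to reproduce.

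**Counting the items (synopsis, Efficacy Data).**

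- All listed items: 7 + 6 + 7 = 20. Without FFR: 19.
- Named groups, broad reading: 11 blood tests (the seven laboratory items, three *C. pneumoniae* tests and hs-CRP), symptoms, NYHA class and pressure/flow indices: 11 + 1 + 1 + 1 = 14. The five left out are QCA and the four imaging items; 14 + 5 = 19.
- Named groups, narrow reading: only the six entries under Biochemistry in Appendix 1 (liver tests, CK-MB, troponin, hs-CRP, electrolytes/urea/creatinine, lipids), plus symptoms, NYHA class and flow indices: 6 + 3 = 9.

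**Formula.** For k independent between-arm tests at 0.05 with no true effect, P(at least one p<0.05) = 1 − 0.95^k. For correlated tests I used normal test statistics with a common correlation ρ and integrated numerically over the shared component. The documents give no correlations, so the values of ρ are assumptions.

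| k | Basis | ρ = 0 | ρ = 0.2 | ρ = 0.5 |
|---|---|---|---|---|
| 9 | named groups, narrow | 1 − 0.95^9 = 37% | 35% | 27% |
| 14 | named groups, broad | 1 − 0.95^14 = 51% | 48% | 35% |
| 19 | all non-primary items | 1 − 0.95^19 = 62% | 57% | 41% |

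The expected number of false positives is 0.05k, whatever the correlation: 0.45, 0.70 and 0.95 for the three rows.

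**If panels are split.** Five of the 19 items contain several measures: 14 blood-count measures and 6 liver tests (Appendix 1), 4 flow indices named in Section 1.1, 2 lipids (Section 7.2.1.1), and at least 3 electrolyte, urea and creatinine items. That gives 19 − 5 + (14 + 6 + 4 + 2 + 3) = 43 outcomes, and 89% at ρ = 0 or 59% at ρ = 0.5. The documents do not say that analytes will be tested one by one. Some red-cell indices are also calculated from others, so independence is unrealistic here. This shows the direction only.

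**The primary test.** It is one Fisher's exact test, and adding other tests does not change its error rate. With 60/2 = 30 per arm, its exact size is 0.009 to 0.027 for assumed null rates of 10% to 50%, which is below 0.05.

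**Limit of the calculation.** The table describes between-arm tests. For a test of change from baseline, a true change common to both arms is not a 5% event, so the table does not give the error rate of the over-time tests as worded. Where both arms truly change, such tests would be significant more often than 5% of the time without any drug effect.

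**The case against.** Four objections deserve an answer.

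1. *The primary test is already set apart.* This stands. Sections 2 and 3 rank the objectives and define one primary endpoint. Section 11.1 names the primary analysis and gives FFR its own test. The declaration of effectiveness in Section 11.2 is tied to the availability of 60 paired FFR data. A reader might infer that secondary findings rank equally with the primary one, or that the primary error rate is inflated; the documents support neither. What is shared is the threshold and the label.

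2. *Not all 20 items are clearly tested.* This stands in part. The testing sentences name symptoms, arterial flow and biochemical variables. QCA and the imaging items come under the 5% rule only through the general wording about all tests, and intracoronary imaging is a sub-study. Hence the smaller counts of 9 and 14.

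3. *Unadjusted secondary testing is normal in a feasibility study.* It is acceptable when reported as descriptive. Section 11.3 describes the study in that spirit, but no sentence carries this through to the significance rule.

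4. *The over-time wording may intend a between-arm comparison.* Analysis of covariance in Section 11.1 would fit that intention. The text does not say so, and the synopsis names a different method. One clarifying phrase would settle it.

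A reader might also infer that full blood count, electrolytes and liver tests are wrongly listed as efficacy data, because they serve for safety too. The documents do not make that an error. Dual use is a matter of labelling, and white-cell counts bear on the inflammation hypothesis in Section 1.1.

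**Conclusion.** The concern holds as a gap in the wording of the significance rule. Followed as written, the plan lets secondary and exploratory results be called statistically significant with no multiplicity control, in a study that describes itself as hypothesis-generating.

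Its size, for between-arm tests with no true effect, is about 27% to 51% for the groups named for testing and 41% to 62% for all 19 non-primary items, with ρ assumed between 0 and 0.5. Testing panel analytes singly would raise these figures.

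It would be tempting to say that at least one false claim is likely. The documents do not establish that. With 14 items the chance is just above one half only near independence. With 19 items it falls below one half once ρ reaches about 0.35, and with 9 it stays below one half throughout.

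**What to change.** In the synopsis (Statistical procedures) and Section 11.1, state that:

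- the two-sided 5% test and the term statistically significant apply only to the primary between-arm FFR comparison;
- all secondary and exploratory outcomes are reported as between-arm estimates with 95% confidence intervals, labelled exploratory;
- changes from baseline within an arm are descriptive and are not evidence of a drug effect.

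The blood panels can stay in the efficacy list.

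With one confirmatory test, the chance of a false confirmatory claim from that test is at most 5%. The change needs no extra subjects, visits or assays. The price is that secondary results can no longer be headlined as significant.

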1. INTRODUCTION AND STUDY RATIONALE

1.1 Introduction

Coronary artery disease (CAD) describes the pathologic process of accumulation of atheromatous plaques within the walls of arteries responsible for supply of oxygen and nutrients to the myocardium. These plaques usually consist of cholesterol deposits, calcium minerals and various amounts of connective tissue and inflammatory cells, and this atheroma eventually reduces the rate of blood flow to the heart¹. Atheromatous plaques originate from the chronic inflammatory responses to many cytokine stimuli, including oxidized Low-Density Lipoprotein (LDL) particles coming into contact with arterial walls. The consequent damage and accumulation of cholesterol results in atherosclerosis and stenosis of arteries².

CHD events result in approximately 6.9 million deaths each year worldwide. In Australia, CHD remains the leading cause of death and is a major contributor to permanent disability. CHD accounted for approximately 48,500 deaths in Australia in 2008 (34% of all mortalities)³. Whilst CHD is usually diagnosed in its advanced stages, a majority of subjects with CAD remain asymptomatic and demonstrate no visible evidence of the disease before a major cardiac event occurs. The prevalence of CHD increases with age and is gender and lifestyle-related. Available data has shown a higher incidence of CHD amongst those aged over 40 years, and men have been shown to be twice as likely to present with CHD compared to women. Tobacco smoking, hypertension, hypercholesterolaemia, family history, diabetes, lack of physical exercise and significant weight gain are associated with an increased risk of developing CHD⁴.

The presence of cholesterol in plaque has directed research efforts towards the development of various groups of drugs to treat hypercholesterolaemia, together with diets and lifestyle changes. Though increased C-reactive protein (CRP) levels have been associated with increased rates of events, there is debate as to whether the JUPITER [Justification for the Use of Statins in Primary Prevention: An Intervention Trial Evaluating Rosuvastatin] trial supports the concept of therapeutic intervention to “reduce inflammation”⁵. The landmark Canakinumab Antiinflammatory Thrombosis Outcome Study (CANTOS) trial which compared Canakinumab, a monoclonal antibody to the pro-inflammatory cytokine interleukin-1 β , with placebo, showed that anti-inflammatory therapy lead to a significant reduction in cardiovascular events compared to placebo⁶. Certainly there is an established and growing body of evidence suggesting that atherosclerosis is a chronic inflammatory disease. This has led to the exploration of potential instigators and propagators of inflammation being considered, including the concept of a chronic infection in the arterial wall leading to chronic inflammation. Though antigens of several candidate infective agents have been identified antigenically, only *Chlamydia pneumoniae* TWAR has been identified in viable form. Furthermore, *C. pneumoniae* has been shown to be a mediator of foam cell formation laden with lipopolysaccharide, as an infective periphenomenon of the *Chlamydia* infection⁷. Chlamydia terminology has recently been refined and *Chlamydia pneumoniae* has been moved to *Chlamydophila pneumoniae* genus. For the present both terminologies are being used interchangeably.

Chlamydophila pneumoniae

Chlamydophila pneumoniae is an obligate intracellular pathogen which requires another cell in order to complete its replication. *C. pneumoniae* exists as a non-biologically active ‘elementary body’ outside a host, only transforming into a ‘reticulate body’ in endosomes upon phagocytosis and utilises the host’s replication mechanisms for proliferation. The consequent replicate reticulate bodies are converted back into elementary bodies and released for further infection into new host cells⁸.

The presence of *C. pneumoniae* in atheromatous plaque specimens and in vitro animal models have implicated *C. pneumoniae* as a potential infectious agent in the pathogenesis and progression of CAD particularly as there is no commensal form of *C.pneumoniae*. *C. pneumoniae* is a common cause of pneumonia and respiratory infection worldwide and has been shown to infect and propagate in human

smooth muscle and endothelial cells of coronary arteries which can be cultured from circulating macrophages. Antibodies to *C. pneumoniae* have been detected in elevated levels in subjects with atherosclerosis though this is non-specific. Some suggest that coronary arterial infection stems from the migration and proliferation of infected macrophages into the intimal layer of the arterial wall after an initial functional alteration or injury to the endothelium⁹.

While numerous studies have demonstrated the presence of *C. pneumoniae* in atherosclerotic arteries and endarterectomy specimens, a lack of standardisation of current diagnostic methods may be responsible for inconsistent detection of *C. pneumoniae*. Indeed detection methods have been largely concentrated on serological studies due to the complexity and difficulty in obtaining tissue cultures. However, accumulating evidence indicates that detection through serological investigations has not been as specific as previously assumed¹⁰. Although cell culture studies remain the gold standard in *C. pneumoniae* detection, isolation and proliferation of *C. pneumoniae* in tissue samples remain a difficult problem resulting in inconsistent results¹¹.

Current Treatment

In subjects with stable coronary heart disease (CHD) and inducible ischemia, percutaneous coronary interventions (PCI) can improve symptoms. As coronary angiography is often inexact in accurately determining the functional significance of non-critical coronary stenoses, fractional flow reserve (FFR) can assess their physiological significance¹². For subjects with acute coronary syndromes and multivessel disease undergoing an early invasive strategy, performing PCI in the culprit vessel and 'staging' possible treatment allows measurement of non culprit FFR at initial angiography. While non-culprit FFR in Acute Coronary Syndrome (ACS) subjects may worsen acutely due to endothelial dysfunction, randomisation should minimise confounding. Return for planned staged PCI as guided by angiography has been standard practice in such subjects, and increasingly, revascularisation is FFR guided. We plan to perform another FFR study to evaluate flow changes over a three month period.

The coronary circulation is comprised of two major components: the major epicardial coronary arteries which have a capacitance function; and the microvascular circulation comprised of pre-arterioles and arterioles which provide a metabolic interface with cardiac myocytes.¹³ Both components of the circulation have been implicated in coronary ischaemia. By measuring pressure and flow in the epicardial coronary artery, indices to assess the microcirculation can be calculated such as CFR, IMR, HSR, HMR at the same time as calculating the FFR value. This provides a comprehensive physiological assessment of the entire coronary circulation¹⁴. We plan to record pressure and flow indices at the time of measurement of FFR in the culprit and non-culprit arteries.

Intra-coronary imaging such as Intravascular Ultrasound (IVUS) and Optical Coherence Tomography (OCT) allow direct visualisation and characterisation of coronary plaque in vivo.¹⁵ Due to the unique characteristics of the energy source utilised for image acquisition, the resolution and penetration capabilities of IVUS (ultrasound) and OCT (infra-red light) differ. The combination of the two modalities allow for comprehensive assessment of atherosclerotic plaque including: atheroma volume, cap thickness, arterial remodelling, calcification, lipid pool/necrotic core, macrophage accumulation and neovascularisation.¹⁵ Intracoronary imaging has been shown to be safe in routine practice and is able to predict clinical events according to lesion characteristics and improve outcomes following PCI however its routine use is limited by cost and reimbursement.^{15,16} We plan on assessing plaque with OCT and IVUS at the time of initial and staged PCI in the culprit and non-culprit coronary arteries in a sub-study.

Other current treatment methodologies have been directed at reduction of cholesterol accumulation in arteries and hence reduction of the associated inflammation. As such, lipid-modifying therapies have reduced mortality and clinical events¹⁷.

Antibiotics and coronary heart disease

Previous trial designs examining the effects of antibiotics in subjects with CHD have been focused on treatment studies with serological and clinical symptoms as primary endpoints. However previous

trials have not yielded reproducible changes in clinical outcomes, likely due to small subject populations, inadequate dosing, and particularly the *use of a single antibiotic* rather than a multiple treatment drug regimen, coupled with a short duration of treatment¹⁸⁻²².

Results of human trials and meta-analyses performed demonstrate that the use of single antibiotics has little or no beneficial effect in reducing subsequent acute cardiac events¹⁹⁻²². In CLARICOR trial of 13,702 subjects in Denmark, there was evidence of significantly higher mortality rates in subjects who received two weeks of treatment with clarithromycin (Odds ratio 1.45, 95% confidence intervals 1.09 to 1.92; P=0.01)¹⁹. On the contrary, results from the only multiple antibiotic STAMINA trial reported the treatment of 325 subjects directed against *C. pneumoniae* and *Helicobacter pylori* showed a significant 36% reduction in the incidence of coronary events at 12 weeks and 12 months. The effect was independent of the presence of antibody to *C. pneumoniae* or to *H. pylori*²². However the use of combined multiple antibiotics in subjects with CHD has not been investigated. Thus, one cannot entirely exclude the importance of antibiotics in the role of CHD treatment.

